Research Design. A parallel-arm double-blind RCT of 202 women to evaluate DST (decision support tool) with AS as an option (intervention) vs. DST without AS as an option (control) for a hypothetical diagnosis with low-grade DCIS. The primary outcome is treatment choice (binary: AS vs non-AS). Secondary outcomes include: acceptability of the different treatment options; perceived riskiness of the AS option, and pre- vs post-knowledge about DCIS (self-reported). Using the secure web portal REDCap, eligible consented women will complete three phases: randomization, baseline, and endline. Randomization phase: 1:1 randomization to control (surgery options only) or intervention (surgery options plus active surveillance option) arms, stratified by age group (< 65, 65+) to ensure balance of age-specific mortality risks. Block randomization (k=6) will be used. Baseline phase: all women will receive information about a hypothetical DCIS diagnosis and complete: 1) a baseline questionnaire about breast cancer and DCIS knowledge. Endline phase: after self-directed exploration of provided content, primary and secondary outcomes will be measured by questionnaire. A series of additional covariates and personality scales will also be elicited with the questionnaire. Each woman is expected to take at most one hour to complete the entire study task. In addition to the questionnaire, the team will collect basic website user analytics such as the order in which the website is explored, and how long participants spend on each page. Eligibility. Consented female participants of age 50-79 years, with no history of breast cancer and with a negative mammographic screen within the preceding 12 months. A financial incentive will be provided. Beta-testing. Before roll-out of the RCT, beta-testing of the evaluation will be conducted in 30 women (15 in each trial arm).

Expected Outcomes. An RCT-validated DA that improves understanding of the trade-offs associated with different management strategies for DCIS, and that increases acceptability of AS as a viable management strategy.

Rigor and Transparency. Rigor in DA evaluation is achieved by using a parallel-arm, double-blind randomized controlled trial design. Highest possible robustness and transparency of the approach will be achieved by registering the trial with clinicaltrials.gov and adhering to CONSORT guidelines for analysis.

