Aim R3: Stage 2: Implement an RCT to test the main hypothesis that the use of personalized decision aids leads to (i) an increase in the proportion of women who would consider active surveillance as a viable management strategy for DCIS, and (ii) an increase in knowledge of the associated risk trade-offs.

C. Research Questions

Primary

[figure not shown]
Compared to presenting active monitoring (AM) as an experimental option, does presenting AM as a guideline-concordant care option increase its uptake as treatment choice?

Secondary

Compared to presenting active monitoring (AM) as an experimental option, does presenting active monitoring as a guideline-concordant care option increase AM acceptability, decrease perceived AM riskiness, and decrease uptake of mastectomy as treatment choice?

D. Study Design

Two-arm parallel randomized controlled clinical trial stratified by age (<65 vs. ≥ 65). Block-randomized in both age strata, with block sizes of n=6.

Control: Decision tool with AM:

- AM portrayed as experimental approach currently evaluated in clinical trials
- Contains in-depth information about the 3 surgical options only

Intervention: Decision tool with AM:

- AM offered as standard of care alongside lumpectomy, lumpectomy with radiation, and mastectomy
- Contains in-depth information about all 4 options

Primary data collection with healthy trial participants. All measures, except for participant age, are self-reported. Participants complete a baseline survey prior to randomization (Decision tool with or without AM), use the Decision tool, and then complete a post survey immediately after. The entire session is expected to take less than 1 hour to complete.

E. Sample Size & Randomization

Prior information

- COMET study team poll (n=4): Intervention uptake of AM estimated to be ~15%
- Patient advocate poll (n=10): Intervention uptake of AM estimated to be ~35%

- Currently, <3% of patients do not undergo surgery after diagnosis with DCIS (any type of DCIS)
- Usability testing (much closer to intervention than control version, n=19): uptake ~40%

Targets

- Assume control arm has AM uptake of ~5%
- Difference intervention vs control is thus ~10% (COMET study team) to ~30% (patient advocates)
- Clinically meaningful difference is ~15%
- We want to calculate sample size for $\Delta=15\%$ (control at 5%, intervention at 20%) at significance level $\alpha = 0.05$ and $\geq 90\%$ power

Calculations:

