H1: Participants who receive in-depth AM information are more likely to choose AM post-tool compared to participants in the control group.

Secondary Outcome 1: Post-tool acceptability of the different treatment options. Measured as categorical 5-point Likert scale from “Not at all comfortable” (1) to “Very comfortable” (5); analyzed as continuous variable. The following question is repeated four times, each time substituting OPTION X for one of the four treatment options:

- Q2.1: How comfortable would you be with **OPTION X** as your initial treatment for DCIS?

H2.1: Participants who receive in-depth AM information report higher AM acceptability compared to participants in the control group.

Secondary Outcome 2: Subjective perception of active monitoring riskiness. Measured as categorical 5-point Likert scale from “Not at all likely” (1) to “Very likely” (5); analyzed as continuous variable.

Q2.2: If you choose active monitoring as your treatment, how likely is it that your DCIS will progress to invasive cancer within 10 years after diagnosis?

- (1) Not at all likely
- (2)
- (3)
- (4)
- (5) Very likely

H2.2: Participants who receive in-depth AM information perceive AM to be subjectively less risky than participants in the control group.

Secondary Outcome 3: Post-tool mastectomy choice. Presented to participants as a categorical item: active monitoring, lumpectomy, lumpectomy with radiation, mastectomy. Recorded for analysis as binary: mastectomy vs non-mastectomy.

Q2.3: see Q1

H2.3: Participants who receive in-depth AM information are less likely to choose a mastectomy compared to participants in the control group.

Secondary Outcome 4: Change in self-perceived knowledge about DCIS. Measured pre- and post-tool as a categorical 5-point Likert scale from “I know very little about DCIS” (1) to “I know a lot about DCIS” (5); analyzed as continuous variable.

Q2.4: How much do you know about ductal carcinoma in situ, abbreviated as DCIS?

- (1) I know very little about DCIS
- (2)
- (3)
- (4)
- (5) I know a lot about DCIS

H2.4: In both groups, self-perceived knowledge about DCIS is higher post-tool compared to pre-tool.

H. Exploratory Aims

See next sections for details about covariates and additional scales used in the explanatory aims.

Exploratory Aim1: Descriptive analyses of the following scales:

- a) DCIS knowledge (11 questions), including AM knowledge (2 questions)
- b) Choice confidence (1 question)
- c) Information needs satisfaction

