- d) Preparation for decision making
- e) Treatment choice reason

Exploratory Aim 2: Does knowledge about AM mediate AM acceptability?

Exploratory Aim 3: Is the score of the minimizer-maximizer scale associated with post-tool treatment choice?

Exploratory Aim 4: Are extreme scores of the minimizer-maximizer scale (1 or 6) associated with less accurate DCIS knowledge?

Exploratory Aim 5: What covariates and personality scales are associated with post-tool treatment choice and AM acceptability?

Exploratory Aim 6: Does subjective perception of AM riskiness mediate choice of AM?

I. Covariates

1) Age: Will be known before participation begins due to the recruitment method; will be used to ensure equal study arm assignment within the two stratification groups. For the analysis we will use self-reported age (years).

2) Race & Ethnicity: Asked as two separate questions

Are you Hispanic or Latina?

- Yes
- No

With which of the following groups do you most closely identify?

- White (1)
- Black or African American (2)
- American Indian or Alaska Native (3)
- Asian or Pacific Islander (4)
- Other (5)

3) SES: 4-level categorical variable

How would you describe your household's financial situation right now?

- After paying the bills, you still have enough money for special things you want
- You have enough money to pay the bills, but little spare money to buy extra or special things
- You have money to pay the bills, but only because you have cut back on things
- You are having difficulty paying the bills, no matter what you do

4) Education: 6-level categorical variable. May be recoded (e.g., college vs no college)

What is your highest level of education?

- Some high school
- High school
- Bachelor's degree
- Master's degree
- Professional degree (e.g., MD, JD)
- Doctorate degree (e.g., PhD)

5) Marital Status: 6-level categorical variable. May be recoded (e.g., married vs not married)

What is your current marital status?

- In Relationship
- Married
- Divorced
- Separated
- Single
- Other

6) Short Graph literacy. Single score derived from 4 items, each scored as correct or incorrect. Correct answers are summed for a total "graph literacy score" (0-4). See "Survey" document for details.

7) Current Health. Self-reported health status (visual analog scale, 0-100%), see "Survey" document for details.

J. Additional scales (See "Survey" documents for details about each scale)

- Choice confidence (Chambers et al., 2012) (post-tool)

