To answer the primary research question, we will use a log-binomial regression model to test the effect of study arm on binary treatment choice (see primary outcome measure), controlling for age group to account for the stratified design:

$$(1) \quad Y_i = \beta_0 + \beta_1 X_i + \beta_2 a_i$$

where

Y_i = subject i 's response: $Y=1$ for AM, $Y=0$ for non-AM choice

X_i = subject i 's study arm: $X=0$ for control arm, $X=1$ for intervention arm

a_i = subject i 's age group: $a=0$ for age <65 years, $a=1$ for age ≥ 65 years

The main effect of interest (1) is represented by β_1 which quantifies the difference in AM uptake between the two arms and will be reported as $\exp(\beta_1)$ with 95% confidence interval [CI].

To follow the CONSORT statement and because the control arm prevalence is expected to be $>10\%$ we will report risk ratios as the relative measure, and absolute risks in both arms.

K.3. Secondary outcome analyses

Secondary Outcome 1. Linear regression model, as in (1), reported as β_1 (95% CI).

Secondary Outcome 2. Linear regression model, as in (1), reported as β_1 (95% CI).

Secondary Outcome 3. Same analysis as primary outcome analysis, reported as β_1 (95% CI).

Secondary Outcome 4. Linear regression model, controlling for age group, and with random intercepts to account for within-subject dependence.

Model:

$$(1) \quad Y_{ij} = \beta_0 + \beta_1 X_i + \beta_2 t_j + \beta_3 t_j X_i + \beta_4 a_i$$

where

Y_{ij} = subject i 's response at time t_j . (0=surgical; 1=AM)

t_j = time (0=pre-tool; 1=post-tool)

X_i = subject i 's study arm (0 = control; 1 = intervention)

a_i = subject i 's age group: $a=0$ for age <65 years, $a=1$ for age ≥ 65 years

If the models for secondary outcomes 1-4 do not meet the required assumptions for linear models, we will explore using median regression and/or dichotomizing the continuous variable (e.g., top quartile=high, remaining values=normal/low).

K.4. Exploratory aims analyses

Ad hoc statistical analyses will be performed for exploratory aims 1-4. For Exploratory Aim 5 (association of covariates and additional scales with choice), we will extend the model (1) to include covariates and additional scales as outlined sections I and J above. The additional model features will first be assessed for multicollinearity, with features removed if necessary. We will do model building to identify a final model, and present both unadjusted and adjusted parameter estimates for the final model (Table 3).

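### Part (ii) of the main hypothesis, knowledge of risk trade-offs, has no declared between-arm hypothesis or reported contrast, and the SAP K.3 model for the knowledge outcome defines its response variable wrongly

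*SAP*

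**What the plan says.** - **Hypothesis.** Protocol (Purpose of the Study; Design & Procedures) and SAP B (Aim R3) give the trial a two-part main hypothesis. The second part is "ii) an increase in knowledge of the associated risk trade-offs".
- **Research questions.** The secondary question in SAP C asks whether the intervention will "increase AM acceptability, decrease perceived AM riskiness, and decrease uptake of mastectomy as treatment choice". Knowledge is not mentioned.
- **Declared outcome.** Protocol, Research Design, lists "pre- vs post-knowledge about DCIS (self-reported") among the secondary outcomes. In SAP G this becomes Secondary Outcome 4, a single 1-5 self-rating taken before and after the tool and treated as continuous. Its hypothesis is "H2.4: In both groups, self-perceived knowledge about DCIS is higher post-tool compared to pre-tool". H1 and H2.1 to H2.3 all compare arms.
- **Analysis.** For Secondary Outcomes 1 to 3, K.3 says that β1 with 95% CI will be reported. For Secondary Outcome 4 it gives "Linear regression model, controlling for age group, and with random intercepts to account for within-subject dependence", with terms for arm, time, arm by time and age group. It names no coefficient to report and codes the response as "0=surgical; 1=AM".
- **Objective knowledge.** "DCIS knowledge (11 questions), including AM knowledge (2 questions") falls under Exploratory Aim 1, which is descriptive. Aim 2 asks "Does knowledge about AM mediate AM acceptability", and Aim 4 relates knowledge accuracy to extreme minimizer-maximizer scores. K.4 leaves Aims 1 to 4 to ad hoc analysis.
- **Arms.** Under SAP D both arms use a decision tool. Control presents AM as experimental and gives depth on the three surgical options. Intervention presents AM as standard and gives depth on all four.

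**The concern.** A randomised trial supports a claim about its intervention through the contrast between arms. For part (ii) the plan states no such contrast as a hypothesis and commits to reporting none. What it does state, H2.4, would be expected to hold for almost any informative website: participants read about DCIS and then rate themselves as knowing more. That rise is not controlled for repeated questioning or for the tendency to report having learned something. The item also asks about DCIS in general, not about trade-offs, and about confidence in one's knowledge, not its accuracy.

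At stake is the statement in Protocol, Expected Outcomes, that the trial will deliver an RCT-validated aid that improves understanding of trade-offs. If H2.4 is met in both arms and cited for that statement, an uncontrolled pre-post change will have been presented as a randomised finding. The survey also collects objective answers that bear more directly on trade-offs, but their comparison between arms is left to ad hoc choice.

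**Working it through.** **1. What each coefficient in the K.3 model means.** With time coded 0/1 and arm coded 0/1, and the response taken as the 1-5 score:
- change in control = β2
- change in intervention = β2 + β3
- difference in change between arms = β3

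H2.4 asserts β2 > 0 and β2 + β3 > 0. Both hold when β3 = 0 and β2 > 0, so confirming H2.4 carries no information on whether the arms differ. A between-arm contrast of self-rated knowledge can be estimated from the model as written; it is simply not declared. With the response coded as printed the model would describe treatment choice, which is not asked before the tool, so there would be no pre-tool value to model.

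**2. Could another declared hypothesis fill the gap?** H2.2 compares arms on the perceived chance of progression under AM within 10 years, which is one side of the trade-off. It predicts that the intervention arm will see AM as less risky. A shift in that direction may be towards or away from the correct figure, so H2.2 tests direction of perception and not accuracy of knowledge.

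**3. What the survey offers.** Protocol Appendix 1 contains 11 objective items after the tool. Two are choose-all items and four name active monitoring. SAP H counts two AM items without identifying them. The completion check in SAP E requires both self-ratings but does not list the objective items.

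**4. The plan's own figure.** SAP E gives 90% power for 5% versus 20% with n = 101 per arm, two-sided 0.05 (assumed). The mean rate is 0.125.
- z = [0.15·√101 − 1.960·√(2·0.125·0.875)] / √(0.05·0.95 + 0.20·0.80) = (1.5075 − 0.9167)/0.4555 = 1.297
- power = Φ(1.297) = 90.3%, which reproduces it.

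This concerns the primary outcome only. The documents give no effect size, SD or power for knowledge.

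**5. Precision for knowledge, in SD units (two-sided 0.05, noncentral t).**
- Objective score by arm, n = 101: half-width = t(0.975, 200)·√(2/101) = 1.972·0.1407 = 0.277 SD. Detectable difference at 80% power is 0.396 SD (normal approximation: 2.80·0.1407 = 0.394).
- If unanswered items left 81 per arm (assumed, with no imputation): 0.310 and 0.443 SD.
- β3, with SD of change = √(2(1−ρ)) and ρ assumed:

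| ρ | SD of change | 95% CI half-width | detectable, 80% power |
|---|---|---|---|
| 0.3 | 1.183 | 0.328 | 0.469 |
| 0.5 | 1.000 | 0.277 | 0.396 |
| 0.7 | 0.775 | 0.215 | 0.307 |

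**6. Illustration of step 1.** With β3 = 0 and an assumed true rise of 0.4 SD, H2.4 is confirmed in both arms with probability 0.846, 0.957 and 0.999 at ρ = 0.3, 0.5 and 0.7. In a simulation of 2,000 trials with equal gains on the 1-5 scale, H2.4 was met in all of them, while a between-arm test of change rejected in 4.75%, close to its nominal 5%.

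**The case against.** The strongest reply is that part (ii) concerns the use of decision aids and both arms use one. No contrast between these arms can show the effect of an aid against none, so no such test was left out. On that view a rise in both groups is a coherent reading of the aim, and it matches the outcome declared in the Protocol. This stands as far as it goes. It means that the added comparison cannot rescue the broad claim, and that the claim itself must be narrowed. It does not turn an uncontrolled rise into a randomised result.

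Other points that stand:
- A reader might infer that the plan contains no between-arm information on knowledge at all. That goes too far: β3 is in the model and SAP Table 2 shows change by arm. What is missing is a declared hypothesis and a commitment to report the contrast.
- A reader might infer from Table 3 that knowledge was singled out for omission. The documents do not support this. The shell also lacks a mastectomy row, and the list of tables describes Table 3 as covering the primary outcome only.
- The response coding looks like a carry-over from a choice model. SAP G and the words linear regression make the intent clear, so an analyst would probably not be misled.
- A total objective score is a blunt measure. SAP D describes no difference between arms in content on the surgical options, so items on those options dilute the ones on which the arms differ.
- K.5 already addresses unanswered variables, and the survey documents cited in SAP J may hold a scoring key.

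**Conclusion.** The point holds. Part (ii) has no declared between-arm hypothesis or reported contrast, H2.4 cannot serve as one, H2.2 does not replace it, and the response in the K.3 model is wrong as written. Severity is minor to moderate. The primary outcome, its log-binomial model and the sample size are untouched.

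The probabilities in step 6 should not be read as an error rate. They are power to confirm a rise assumed to be true, at assumed effect sizes and correlations. They show only that H2.4 does not discriminate between arms, and they measure no bias. The half-width of about 0.28 SD and the detectable difference of about 0.40 SD rest on 101 analysed per arm and describe precision, since the documents state no expected effect on knowledge.

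**What to change.** 1. In K.3, define the response for Secondary Outcome 4 as the 1-5 self-rated DCIS knowledge score.
2. Report β3 with 95% CI as the between-arm contrast. For H2.4 report β2 (control) and β2 + β3 (intervention), labelled as uncontrolled within-arm changes.
3. Add, as a secondary estimate with 95% CI, a between-arm comparison of post-tool objective knowledge adjusted for age group. Identify the AM and trade-off items and show them separately from the total. Keep the item on which options are used to treat DCIS outside the total, because the arms are told different things about the status of AM. State or cite a scoring key fixed before analysis, including the two choose-all items, and say how K.5 applies to unanswered items.
4. Limit part (ii) and the Expected Outcomes statement to what the arms contrast: AM as a standard option with in-depth information versus AM as experimental, both within a decision tool.
5. Editorially, add knowledge and mastectomy rows to Table 3.

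The cost is wording in both documents, a scoring key and a regression on items that the survey already includes. The downside is one more secondary comparison, which could miss a true difference smaller than about 0.40 SD and is therefore best read as an estimate with its interval. No change to the sample size is needed.

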I confirm that I have finished exploring the Decision Support Tool.

- Yes, I am ready to continue

Below is the link to the last section to explore, the Information Center. It will open in a new window. When you are done exploring, return back here and click 'Next Page.'

Please click the link below and use the following access code: [record-name]

[Click Here \(Link 3 of 3\): Information Center](#)

0%

15%

100%

I confirm that I have finished exploring the three links provided and I am ready to continue the survey.

Yes, I am ready to continue

(If not, please finish exploring the three links; they are provided at the bottom of this page)

Keep in mind, you can revisit any of the sections at any time while completing the survey (your access code: [record-name])

Guide

Decision Support Tool

Information Center

0%

18%

100%

If you were a patient diagnosed with DCIS, what treatment option would you choose?

- Active monitoring
- Lumpectomy
- Lumpectomy with radiation
- Mastectomy

0%

21%

100%

Why did you choose this treatment option? (You may list several reasons)

Please rate, how confident are you in your treatment choice?

- 1 Not at all confident
- 2
- 3
- 4
- 5 Very confident

0%

24%

100%

How comfortable would you be with active monitoring as your initial treatment for DCIS?

- 1 Not at all comfortable
- 2
- 3
- 4
- 5 Very comfortable

How comfortable would you be with lumpectomy as your initial treatment for DCIS?

1 Not at all comfortable
 2
 3
 4
 5 Very comfortable

How comfortable would you be with lumpectomy with radiation as your initial treatment for DCIS?

1 Not at all comfortable
 2
 3
 4
 5 Very comfortable

How comfortable would you be with mastectomy as your initial treatment for DCIS?

1 Not at all comfortable
 2
 3
 4
 5 Very comfortable

If you choose active monitoring as your treatment, how likely is it that your DCIS will progress to invasive cancer within 10 years after diagnosis?

1 Not at all likely
 2
 3
 4
 5 Very likely

Please note: for the rest of the survey when we use the term 'DCIS website', we are referring to the collection of all three links you reviewed (Guide, Decision Support Tool, and Information Center).

After you have reviewed the DCIS website, how much do you know about ductal carcinoma in situ, abbreviated as DCIS?

1 I know very little about DCIS
 2
 3
 4
 5 I know a lot about DCIS

What do you think about the amount of information on the DCIS website?

1 Too little information was provided
 2
 3

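### Exploratory Aims 2 and 6 ask about mediation, but each mediator is recorded after its outcome, so mediation could not be told apart from a reverse effect

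*SAP*

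**What the plan says.** SAP section H lists two mediation questions among six exploratory aims. Aim 2 asks "Does knowledge about AM mediate AM acceptability" and Aim 6 asks "Does subjective perception of AM riskiness mediate choice of AM". The outcome in Aim 6 is the primary-outcome item; the outcome in Aim 2 is part of Secondary Outcome 1.

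SAP section K.4 leaves Aims 1 to 4 to ad hoc analysis, sets out a model for Aim 5 and names nothing for Aim 6. It gives no mediation model, no assumption about temporal order and no check of the reverse direction.

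Protocol Appendix 1 shows the questionnaire. The first item after the tool is "If you were a patient diagnosed with DCIS, what treatment option would you choose". The rating used as the Aim 6 mediator, "how likely is it that your DCIS will progress to invasive cancer within 10 years after diagnosis", comes several items later, and the knowledge test later still. Participants are also told: "Keep in mind, you can revisit any of the sections at any time while completing the survey".

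**The concern.** A mediation analysis reads an association between mediator and outcome as the mediator acting on the outcome. That reading is easier to defend when the mediator is measured first. Here it is measured second. A woman who has just chosen AM and written down why may then rate it as less risky. If the tool raises AM uptake, the intervention arm will show lower perceived risk for that reason alone. Knowledge answers could also change after the acceptability rating if the tool is reopened.

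At stake is a statement about how the tool works. The trial's central hypothesis concerns understanding of trade-offs, so an indirect effect through lower perceived risk or better knowledge would be read as the mechanism. The design cannot support that reading.

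**Working it through.** **Order of the items (protocol Appendix 1)**

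1. Before the tool: self-rated knowledge of breast cancer and of DCIS only. There is no item on AM risk or AM knowledge.
2. After the tool: treatment choice (Aim 6 outcome).
3. Free-text reasons for the choice, then confidence in it.
4. Comfort with each of the four options. The AM item, "How comfortable would you be with active monitoring as your initial treatment for DCIS", is the Aim 2 outcome.
5. Perceived AM riskiness (Aim 6 mediator).
6. Self-rated DCIS knowledge and website ratings.
7. The knowledge test, after the 33% progress marker (Aim 2 mediator).

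SAP section H says that two of the 11 knowledge questions concern AM but does not name them. Every knowledge-test item follows the comfort items, so the order holds whichever two are meant. The only randomized order stated is the note printed with the response options of Q1 in SAP section G; no randomized order of questions is given.

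**The plan's own figure**

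The SAP states no figure for Aims 2 or 6. Its Scenario 1 fixes the sample size used below: 101 per arm, 5% against 20%, 90% power. With a pooled two-sided test at 0.05 and mean uptake 0.125:

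z = [0.15·√101 − 1.96·√(2·0.125·0.875)] / √(0.05·0.95 + 0.20·0.80) = (1.507 − 0.917) / 0.456 ≈ 1.30, giving power of 90.3%. The figure reproduces.

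**What a purely reverse effect looks like (Aim 6 only)**

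Assume that arm changes choice by Δ, that choosing AM lowers the later rating by d, that the rating otherwise has SD 1, and that the rating has no effect on choice. Let v be the mean over arms of p(1−p).

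- Path from arm to rating: a = −d·Δ
- Path from rating to choice, given arm: b = −d·v / (d²·v + 1)
- Share of the effect that appears mediated: a·b/Δ = d²·v / (d²·v + 1)

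At 5%/20%, v = (0.0475 + 0.16)/2 = 0.10375. At 10%/40% (SAP Scenario 3), v = (0.09 + 0.24)/2 = 0.165. For d = 1 at 5%/20%, the share is 0.10375/1.10375 = 9.4%.

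The simulation used 2,000 trials per setting, 101 per arm, a continuous rating, and a joint test of both paths adjusted for age group:

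| Uptake | d | Share, formula | Share, simulated | Significant |
|---|---|---|---|---|
| 5%/20% | 0 | 0% | 0% | 0.4% |
| 5%/20% | 0.5 | 2.5% | 2.7% | 5.5% |
| 5%/20% | 1.0 | 9.4% | 9.7% | 16.9% |
| 5%/20% | 1.5 | 18.9% | 19.6% | 32.6% |
| 10%/40% | 0 | 0% | 0% | 0.2% |
| 10%/40% | 0.5 | 4.0% | 4.0% | 14.8% |
| 10%/40% | 1.0 | 14.2% | 14.3% | 50.5% |
| 10%/40% | 1.5 | 27.1% | 27.0% | 76.9% |

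With the shift set in points on the 5-point rating (SD about 1 point), the share of trials with a significant product of coefficients is slightly lower. For a shift of 1 to 1.5 points it is about 15-31% at 5%/20% and 46-74% at 10%/40%. For a 0.5-point shift it is about 4-13% across settings. I take these as the headline range because they match the scale of the questionnaire.

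**The case against.** The case on the other side has real force.

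- **Order of asking is not order of forming.** Participants confirm that they have explored all three website sections before any outcome item. Perceived risk and knowledge may already have existed when the choice was made. This stands: the order does not show that a reverse effect occurred.
- **The SAP asks and does not claim.** A reader might infer that the plan asserts mediation, or that a reverse effect would necessarily be reported as mediation. The documents support neither. Both aims are exploratory questions, no mediation method is named, and the table shells have no row for an indirect effect.
- **Aim 2 is the weaker half.** Its mediator is scored factual knowledge, which is less open to after-the-fact justification than a subjective rating. The argument there rests mainly on reopening the tool, which is allowed but of unknown frequency. The page-order and time-on-page data described under Research Design in the protocol might show how often it happens.
- **The simulation assumes what it finds.** It builds in only a reverse effect, of a size the documents do not give, and tests a method the SAP does not specify. It shows what is possible, not what is likely.
- **Asking about risk first would not settle direction.** The mediator is not randomized, so confounding would remain. This is a reason to leave the survey order alone.

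None of this lets the data separate the two directions. Neither mediator has a baseline value, and the plan has no assumption or check that would do so.

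**Conclusion.** The point holds in a limited form: a reverse effect could not be distinguished from mediation in Aims 2 and 6, and could be reported as such. It is stronger for Aim 6 than for Aim 2, for which I give no size.

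The Aim 6 figures rest on an assumed shift, an assumed rating SD of about 1 point, no true mediation and a product-of-coefficients analysis. At the design uptake of 5%/20%, even a large reverse effect leaves most trials without a significant result. The higher range needs the 10%/40% scenario.

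The item order comes from the protocol dated November 2022. The SAP is dated October 2021, and the separate survey document it refers to is not available, so Appendix 1 is the only order documented.

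The issue is minor. Sample size and the primary and secondary results are untouched.

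**What to change.** Leave the survey order as it is and change the SAP text:

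1. Reword Aim 6 as: *Is perceived AM riskiness associated with AM choice, adjusting for arm and age group?* Reword Aim 2 as: *Is AM knowledge associated with AM acceptability, adjusting for arm and age group?* Aims 3 to 5 are already framed as associations.
2. Name this analysis for Aim 6 in K.4, where none is given now.
3. State that neither result will be interpreted as an indirect effect or a proportion mediated, because each mediator was recorded after its outcome and direction cannot be established.

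If the sponsor prefers to keep a mediation estimate, the SAP should state the temporal-order and no-confounding assumptions. The reverse-direction model and a sensitivity analysis should then be reported beside the estimate.

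The cost is SAP wording, plus the loss of a mechanistic reading of two exploratory aims. No new data and no survey change are needed.
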